There is no clear consensus regarding appropriate control conditions to use in alcohol reduction app (Staiger, O'Donnell, Liknaitzky, Bush, & Milward, 2020) or ApBM research (Kakoschke, Kemps, & Tiggemann, 2018). In designing our control condition, a primary consideration was controlling for the effect of self-monitoring, since the data collection aspects of AAT-App involve regular self-report of alcohol use, and such self-monitoring behaviours may themselves assist with reducing alcohol use (Michie et al., 2012). To control for this effect, and thereby ensure that we can specifically attribute any positive effects to the inclusion of ApBM training (and not merely the effects of the data collection, which may not be present in a final version of the app that would be implemented clinically), the control version of the app includes the same self-report requirements as the ApBM version. A second consideration was ensuring blinding: if participants in the control condition know they are in a control condition, this may bias outcomes both due to expectancy effects and due to differential rates of drop-out (as participants may be less likely to remain motivated to continue participating if they know they are not receiving an intervention). If control participants were only asked to self-report weekly alcohol use, it is likely they may guess they are not in an intervention condition and, as such we have included a weekly sham-training task (which also functions as an approach bias measurement task), so that participants in both conditions can be told they are completing an “attention control” task.

Aims and Hypotheses

We aim to determine whether providing the “active” version of AAT-App (including ApBM) to people accessing outpatient alcohol treatment from AOD services, is effective, relative to a minimal version of the app which does not include ApBM training, at reducing alcohol use, cravings, and severity of dependence. We also aim to test the psychometric properties of the mobile phone approach bias measure we developed, and whether engaging in AAT-App significantly reduces approach bias, relative to the minimal control condition. We also aim to explore user experiences of AAT-App’s, perceived alignment with treatment, and suggested improvements, using qualitative interviews in a subset of participants, to guide further future improvements to the app and its implementation.

We hypothesise that:

Primary outcome:

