week standard drinks will therefore be calculated using the sum of values entered for each of the past 7 days, and past-week drinking days will be derived from the number of days in the past week for which the participant provided a non-zero value for standard drinks. Participants will then be shown the calendar chart with the previous week highlighted (8-14 days ago), where they will be asked to select a number ranging from 0-7 to indicate their estimate of how many days they consumed alcohol in that week. This will then be repeated with the previous week (15-21 days ago) and then the week previous to that (22-28 days ago). Baseline past-month drinking days will be calculated by summing past-week drinking days with the number of drinking days indicated for each of the 3 preceding weeks. The app will automatically prompt participants to repeat the past-week standard drinks assessment 7, 14, 21, and 28 days after they complete this baseline assessment, to provide complete standard drink and drinking days data for the intervention period. Drinking assessments at 1-month and 3-month follow-ups will be identical to the baseline assessment. The past-week drinking assessment closely resembles the computerised 7-day timeline follow-back assessment used by Simons, Wills, Emery, and Marks (2015), which showed 87% concordance with an objective transdermal measure of alcohol use in terms of drinking days.

Alcohol approach bias: At baseline and post-test, participants will be required to complete an adapted, irrelevant-feature, smartphone version of the alcohol approach-avoidance task (AAT) (R. W. Wiers, Rinck, Dictus, & van den Wildenberg, 2009). Each session of the AAT is immediately preceded and followed by the VAS craving measure. Participants in the minimal condition will also complete 3 additional sessions of the AAT at the end of week 1, week 2 and week 3 (directly after completing the weekly alcohol consumption questions at each timepoint) in order to maintain blinding.

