Minimal (control) group: Control participants will receive a minimal version of AAT-App which does not include any ApBM training or picture selection component, and only includes the weekly alcohol consumption questions, a weekly AAT task, and the VAS craving measure. Upon opening the app for the first time, participants are informed that they will be using "an app designed to target their alcohol use and awareness". Instead, participants are told that the "brain-training" will involve completing one training task at the end of each week, and answering some questions about their weekly alcohol consumption.

After reading the opening page's instructions, participants will then complete the alcohol consumption questions, before completing the pre-training VAS, the AAT, and the post-training VAS. The VAS is included so that cravings can be monitored before and after completing the AAT, where participants can access additional support if they indicate that their cravings are extreme (i.e., through links to Counselling Online and the National Alcohol and Other Drug Hotline). At the end of week 1 (i.e., 7 days post-baseline) participants will receive a notification reminder to complete the weekly alcohol consumption questions, followed by the pre-training VAS, AAT and post-training VAS. This process is repeated at the end of each week throughout the intervention period (i.e., 14-, 21- and 28-days post-baseline).

Procedure: Staff at participating services will briefly describe the study to clients who they believe may meet eligibility criteria. To allow for blinding, no specific details will be provided regarding approach bias modification, and participants will merely be informed that the study tests "a new smartphone 'brain-training app'" that "involves doing brief game-like tasks on your phone each week for 4 weeks". Clients who are interested will be asked to sign a form providing consent for the treatment service to provide their phone number to research staff. In the event they are unable to sign the form (e.g., if not present in person due to a telehealth appointment), clients can give verbal consent for the clinician to sign the form on their behalf. Clinicians can also complete the form online via Qualtrics Plus, by scanning a QR code on the paper form which directs them to an online

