Participants will be required to indicate that they have read and understood the information and consent to participate. This will result in the remaining baseline questionnaires being displayed including items assessing gender, which AOD treatment service the participant is attending, type(s) of treatment being accessed, drugs of concern, date of commencement of the current episode of treatment, treatment goal (abstinence or moderation), SDS, CEQ-F, and ATOP quality of life items. They will also be required to enter their smartphone number, and are encouraged to enter additional contact details (e.g., name, email, other phone numbers, and postal address) to assist with ensuring follow-ups are completed, although this is not required.

Completing the Qualtrics survey will result in an email being automatically sent to researchers, who will access the list of access codes, select the first unused code, and send the download link and access code to the participant via SMS. The researcher will record which access code was sent to which phone number. Once participants have downloaded the app, they will be prompted to enter the access code, thus resulting in either the ApBM or minimal version of the app being installed on their phone. Participants in the active condition will view a short introductory animation explaining how the ApBM intervention works, while participants in the minimal condition will be onboarded through written text that ensures blinding is maintained (see details provided above). Participants will then be required to complete the baseline alcohol consumption questions, before completing the pre-training VAS craving measure, the AAT, and the post-training VAS craving measure. Participants in the active condition will then proceed to the image selection feature, where they will be prompted to upload or select 6 alcohol-related images and 6 positive images to be used in the ApBM training task. These participants will then complete the pre-training VAS craving measure, their first session of the ApBM task, and the post-training VAS craving measure.

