Participants in the active condition will be instructed to complete at least 2 sessions of the ApBM training task (approximately 3-5 minutes in duration) each week for the duration of the 4-week intervention period, though they can complete more sessions if they wish (via a "more training" option in the app's homepage). Participants in the minimal condition will not complete any ApBM sessions. At the end of each week throughout the intervention period (i.e., 7-, 14-, 21- and 28-days post-baseline) participants will complete the weekly alcohol consumption questions. Participants in

the minimal condition will also complete the AAT (preceded and followed by the VAS craving measure) immediately after the alcohol consumption questions at each 7-day timepoint (which they will be told is an “attention training task”, to maintain blinding), while participants in the active condition will only complete the AAT again at the 28-day post-baseline timepoint. There will be no limitation on concomitant care/interventions that participants can commence during the intervention period (or the following follow-up period).

After completing the 28-day post-baseline alcohol consumption questions and AAT, participants in both conditions will be provided with an in-app link to a post-test Qualtrics survey which includes SDS, CEQ-F, ATOP items, and ratings of the app’s acceptability. The questionnaire will also ask if they have undergone any residential/inpatient treatment (e.g., residential rehabilitation, withdrawal treatment, or hospitalisation) in the past 28 days and, if so, will ask how many days they spent entirely within residential treatment (i.e., with no opportunity to drink alcohol), whether any of these days were in the past week, and, if so, how many. Participants will be reimbursed with a \$20 supermarket voucher for completing the post-test Qualtrics survey within 1 week (the link will expire after this point).

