Audio-recorded qualitative interviews and verbal consent will be stored as .mp4 files on a secure Google drive hosted by Monash University, access to which will be restricted to project personnel (but which will not be made accessible to blinded quantitative data collectors until data collection is complete). The .mp4 files will be securely transferred to Pacific Transcription, a trusted transcription service provider that is frequently used by Monash University and Turning Point. To preserve participant anonymity the recording of verbal consent (where the participant states their full name and is also asked about their phone number) will be separated from the rest of the file and stored separately, while the main interview file will be labelled with a participant number (this number will be the same as the participant access code used to access the app, allowing baseline demographic data to be matched to qualitative interview data), not their name. Transcripts returned by Pacific Transcription will be stored as .docx files on the secure Google drive until data collection is complete. Once data collection is complete and blinding no longer required, these files will be stored in the project folder on the Turning Point Clinical Research Drive. They will be deleted from the Google Drive once analysis and publication is complete, and stored for at least 7 years following publication of the last paper arising from this study, or 7 years after the final report to the ethics committee, or 7 years after final reporting of outcomes on the clinical trials registry, whichever occurs latest.

Data Analysis

Statistical significance will be ascertained using $\alpha=.05$. Any participants who commenced at least 1 session of ApBM (if in the ApBM condition) or AAT (if in the minimal control condition) will be included in the analysis population.

Primary outcome: A linear mixed-effects model (LMM) will be used to compare change in mean standard drinks consumed per week between groups across 4 time points (baseline, post-intervention, 1-month follow-up, and 3-month follow-up). This model will test the main effects of time and group and (most crucially for determining efficacy) the group x time interaction. Planned follow-up comparisons between groups at post-intervention, 1-month follow-up, and 3-month

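### The analysis set has a different post-randomisation entry event in each arm: a person who starts the baseline AAT but never starts ApBM is analysed if control and dropped if active

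*Combined protocol and SAP*

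**What the plan says.** The Data Analysis section names one analysis population: "Any participants who commenced at least 1 session of ApBM (if in the ApBM condition) or AAT (if in the minimal control condition". No other population is defined.

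The AAT has two roles. The paragraph on the control condition, just before Aims and Hypotheses, says "we have included a weekly sham-training task (which also functions as an approach bias measurement task". Under Minimal (control) group, on first opening the app "participants will then complete the alcohol consumption questions, before completing the pre-training VAS, the AAT, and the post-training VAS". The Procedure section prescribes the same opening sequence for both arms and then adds steps for one: "Participants in the active condition will then proceed to the image selection feature", and after that "These participants will then complete the pre-training VAS craving measure, their first session of the ApBM task". The active arm's next AAT is much later: "participants in the active condition will only complete the AAT again at the 28-day post-baseline timepoint".

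Allocation comes before all of this. The access code is sent by SMS once the baseline survey is complete, entering it installs one version of the app, and "The researcher will record which access code was sent to which phone number".

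Under Measures (Alcohol consumption), baseline drinking is recorded in the app, which will "prompt participants to repeat the past-week standard drinks assessment 7, 14, 21, and 28 days after they complete this baseline assessment".

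The only sensitivity analyses in the Data Analysis section concern residential or inpatient stays.

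**The concern.** The rule can be read as a single principle: analyse whoever began the allocated task. The two entry events are not equivalent, however. The control event is the shared baseline assessment. The active event is strictly later and lies behind steps that controls never face. Both follow randomisation.

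People who would stall between the AAT and ApBM should be equally common in the two arms. The rule removes them from the active arm and keeps them among controls, so randomisation no longer fully protects the comparison. If they drink like everyone else there is no bias. If they drink more, the result favours ApBM; if they drink less, it goes against ApBM.

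The rule also fits poorly with the stated aim, which concerns the effect of providing the active version of the app. Picture selection is part of what is provided.

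**Working it through.** **Order of events (Procedure section)**

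| Step | Active | Control |
|---|---|---|
| Access code sent, arm fixed | yes | yes |
| Onboarding | animation | text |
| Baseline drinking questions | yes | yes |
| VAS, AAT, VAS | yes | yes; **enters the analysis set on starting the AAT** |
| Choose 6 alcohol and 6 positive pictures | yes | none |
| VAS, first ApBM session | **enters the analysis set on starting ApBM** | none |

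An active participant who stops after the AAT already has baseline drinking data, yet is excluded unless they start an ApBM session at some later time. A control who stops at the same point is included.

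**The plan's own figure.** The Participants section gives 90% power with 178 participants for an interaction with partial eta squared .01 over 4 measures. The correlation is not stated. Assuming 0.5 and sphericity, λ = 178 × 4 × (.01/.99)/(1 − 0.5) = 14.38. On F(3, 528) at α = .05 the power is .902, so the figure reproduces. The asymmetry does not alter this calculation. I use 178 (89 per arm) and correlation 0.5 below; 178 is the number required, not a forecast.

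**Assumptions not in the documents.** Let q be the share of would-be non-starters among controls with outcomes, and d their difference in drinking from the others, in SD. There is no true effect and tests are two-sided. The documents give no rate of non-starting; the pilot figures in the introduction count only people who had already begun using the app.

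**Level comparison (post-intervention t-test).** Bias b = q × d, SE = √(2/89) = 0.150, non-central t with 176 df.

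| q | d | b (SD) | Type I error |
|---|---|---|---|
| 5% | 0.2 | 0.010 | 5.05% |
| 5% | 0.5 | 0.025 | 5.3% |
| 10% | 0.2 | 0.020 | 5.2% |
| 10% | 0.5 | 0.050 | 6.3% |
| 20% | 0.2 | 0.040 | 5.8% |
| 20% | 0.5 | 0.100 | 10.2% |

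These keep 89 in each arm. If the active arm is also reduced by the 20% excluded, a normal approximation gives 9.6% for the last row. With 300 participants in place of 178, it gives 12.9%.

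**Group by time interaction (3 df, compound symmetry).** A difference that is constant over time cancels, leaving 5.0%. If it arises only after baseline, λ = (89/2) × 0.75 × b²/(1 − ρ). This holds whether b is present at all three later times or at post-intervention only. At ρ = 0.5:

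- b = 0.010: 5.04%
- b = 0.020: 5.2%
- b = 0.050: 6.0% (5.7% at ρ = 0.3, 6.7% at ρ = 0.7)
- b = 0.100: 9.2%

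**What inclusion alone would recover.** Assume 10% would-be non-starters, with controls and active starters reporting at 59% (the plan's retention figure). If active non-starters report at 20%, their share of the observed active arm is (.10 × .20)/(.10 × .20 + .90 × .59) = .0363, against .10 among controls. An observed-data comparison then keeps (.10 − .0363)/.10 = 64% of the level bias, that is 0.013–0.032 SD in place of 0.020–0.050 SD. Reporting at 40% leaves 30%, and at 59% none. At 0% all of the bias remains.

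**The case against.** The group that creates the bias is narrow. It needs a person who, if active, would never start a single session, although picture libraries are supplied, the session follows directly and there is no deadline. The same person, as a control, must still report drinking at day 28. Nothing in the documents supports a share as high as 20% among controls with outcomes. If 10% of those randomised are of this type and report at 20–40% as controls while others report at 59%, they form 3.6–7.0% of reporting controls. At 0.5 SD, type I error is then 5.2–5.6%. The test that the plan treats as decisive, the interaction, is untouched by a constant difference.

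It is also not established that someone stuck at picture selection can reach the later in-app drinking questions. The day 7–28 prompts are tied to the baseline assessment, but access is not described. If they cannot, the excluded active participants have only baseline drinking data, and changing the analysis set would leave the whole level bias in an observed-data t-test.

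All of this stands as to weight: the upper figures above rest on assumption and should not drive the priority given to the point. None of it removes the asymmetry. The rule still excludes people by arm after randomisation, and no planned analysis would reveal or bound the effect.

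**Conclusion.** The concern holds. As written, the analysis population builds in an arm-dependent exclusion after randomisation. That follows from the text alone and is certain. Direction and size are unknown. Under the assumed shares and differences the bias is 0.01–0.10 SD, with type I error of 5.05–10.2% for the post-intervention comparison and 5.0–9.2% for the interaction at correlation 0.5. With a 10% share the upper values are 6.3% and 6.0%. The effect is negligible if few people stall or if they drink like the rest. The point should be fixed because it touches the primary comparison and every secondary outcome analysed in this population, and because correction is cheap.

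**What to change.** - Define the primary analysis set as all randomised participants (access code issued), analysed as allocated, with all available data in the mixed model. For the primary outcome, those with in-app baseline drinking data or any later report then contribute.
- If a modified set is preferred, use one milestone identical in both arms before the tasks diverge: completion of the in-app baseline alcohol questions. Note that onboarding already differs by then.
- Keep the current set as a labelled secondary analysis.
- Report losses by arm at each step: code issued, baseline questions completed, AAT started, ApBM started.
- State whether a participant who stalls at picture selection can still reach the later drinking questions.
- State that the change removes the arm-dependent exclusion but not bias from differential missing outcomes, which still rests on the mixed model's missing-data assumption. If excluded active participants report nothing after baseline, the follow-up t-tests on observed data gain nothing.

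The cost is wording in the analysis plan and one participant-flow table. No new data are needed: the researchers' record of codes sent gives the randomised denominator, and the app data listed under Data management give the in-app steps. The downside is a few more participants with sparse data and perhaps a slightly diluted estimate.

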Design & Setting: We will conduct a double-blind, randomised, parallel-group controlled superiority trial with alcohol treatment outpatients at 6 AOD treatment services in Melbourne, Victoria. Participants will be randomised to one of 2 groups with a 1:1 allocation ratio. Both participants and researchers completing the follow-up interviews will be unaware (blinded) of the condition to which they have been randomly allocated.

Participants: We aim to recruit at least 300 participants receiving outpatient interventions for alcohol use disorder at the participating services. To be eligible, participants must, at the time of the screening interview:

- Be aged 18+
- Own an Android or iOS smartphone with an Australian mobile number
- Be currently accessing outpatient treatment for alcohol problems. (There is no requirement that alcohol be the *only* substance for which they are seeking treatment, and as such participants with multiple drugs of concern are eligible as long as alcohol is one of the drugs of concern for the current episode of treatment.)
- Have an Alcohol Use Disorders Identification Test (AUDIT) score of at least 8
- Not have been in residential rehabilitation within the past 4 weeks.
- Not have been in any form of inpatient treatment (e.g. hospital or residential withdrawal treatment) within the past week.
- Not entering inpatient/residential treatment within the next month.

The target sample size was determined based on practical considerations (likely recruitment rate, time available for recruitment), as there was little prior basis to estimate likely effect size of a personalised ApBM smartphone app in an outpatient client population. Nevertheless, a calculation conducted in GPower 3.1 suggested that the primary analysis (across 4 repeated measures) would have 90% power to detect a small time x group interaction effect size (partial eta squared of .01) with a sample of 178 participants (i.e., 59% retention at follow-ups). If recruitment proceeds quickly enough, we will aim to recruit more than 300 participants, to allow for increased statistical power in case attrition is larger than expected.

Measures:

Demographic information: Participants will be asked to enter their gender, the AOD service where they were recruited from, the date they began the current episode of treatment they are receiving from that service, and drugs of concern, in an online survey hosted on Qualtrics.

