Each item will be rated on a scale from zero to ten, where zero is poor and ten is good. Each rating will be treated as a separate variable in analyses (i.e., no composite score will be derived from the 3 separate items). These items have shown moderate-strong concurrent validity (correlation absolute values ranging from .51-.72) with relevant gold-standard multi-instrument measures of psychological health, physical health, and quality of life (Ryan et al., 2014). Mammen et al. (2021) found that a cut-off score of 5 or below had optimal sensitivity and specificity for indicating clinically significant problems.

App acceptability: At the end of the 4-week intervention period, participants will be asked to complete the "functionality" and "aesthetics" sub-scales and the "app subjective quality" section of the user version of the Mobile Application Rating Scale (uMARS) (Stoyanov, Hides, Kavanagh, & Wilson, 2016). Additionally, participants will have the option to enter free text comments in response to 3 open-ended questions: "What did you like about this app?", "what did you not like about the app?", "any further comments about the app?". Participants will also be asked to rate the statements: "The app helped me reduce my alcohol use", "The app increased my alcohol consumption", "The app helped reduce my cravings for alcohol" and "The app increased my cravings for alcohol". Responses will be assessed using a 5-point Likert scale ranging from "strongly agree" to "strongly disagree".

Qualitative interview: After completing the 1-month follow-up, a representative subset of participants ($n=20$) who had been randomised to the active ApBM condition will be contacted by an unblinded researcher and invited to complete an approximately 30-minute semi-structured qualitative interview about their experiences using the app, its perceived alignment with their treatment, and suggestions for improvement. Interviews will be audio-recorded, and recordings will be transcribed using a trusted transcription service. Participants will be reimbursed with a \$40 supermarket voucher upon completion of the interview. See Appendix 1 for the qualitative interview schedule.

Randomisation and blinding of allocation: Six computer-generated randomisation sequences (one for each recruitment site) will be produced by a data scientist who is not otherwise involved in recruitment or data collection, processing, or analysis, using a 1:1 allocation ratio, based on blocks of

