variable size (ranging from 2-6). As such, randomisation will be stratified by site. The app developers (ANT Development Studios Ltd.) will provide the data scientist with two lists of app access codes which will direct participants to either the intervention or minimal version of AAT-App when they first download and open the app. Using these lists and the randomisation sequence, the data scientist will generate a separate spreadsheet of access codes for each site (based on the site-stratified randomisation sequence). Researchers will send these codes to participants as they are recruited from each respective site. Researchers involved in recruitment will only have access to a spreadsheet displaying a single list of codes to be sent to participants at each respective site, while the randomisation sequence will be stored in a password-protected file provided to the trial statistician and to one research officer who will remain unblinded to assist with coordinating qualitative interviews. Neither the randomisation file, nor its password will be provided to any other staff (including the principal investigator, [name], and research officer, [name]) involved in recruitment or in pursuing follow-ups or quantitative data management until all data analysis is complete.

Intervention: Prior to commencing the intervention, participants will be prompted to select 6 alcohol-related pictures that represent the drinks they most frequently consume. Participants can either select from their own photographs stored on their phone, take photographs of alcoholic beverages using the app, or select pictures from a library of 67 alcohol-related images chosen to represent a broad range of alcoholic beverages commonly consumed in Australia. Participants will then be prompted to select 6 pictures that “represent your goals and motivations”. Again, participants can either select their own photographs, take photographs, or select pictures from a library of 68 pictures representing a range of healthy activities or positive goals and sources of pleasure (including family or friends enjoying time together; financial success; employment; exercise, sports, and recreational activities; healthy foods; pets; travel and holidays) which do not contain any depictions of alcohol. If participants take/use their own photographs, they will be reminded to ensure that positive images do not contain depictions of alcohol.

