follow-up time-points will be conducted using t-tests, with post-intervention being the primary endpoint. A secondary sensitivity analysis will be conducted excluding a participant's data from any time-point where they had been in residential/inpatient treatment in the past week (i.e., restricting analyses to time-points where a participant's opportunity to drink had not been limited by hospitalisation, rehabilitation, etc.). If a difference between groups is found post-intervention, a secondary LMM analysis of difference between groups in change in weekly standard drinks during the intervention period (i.e., 5 levels of time: Baseline, week 1, week 2, week 3, post-intervention) will be conducted to examine how quickly differences between groups emerge, with t-tests used to compare groups at week 1, 2, 3, and post-intervention time-points. This secondary analysis will be conducted excluding participants who had engaged in any residential/inpatient treatment within the intervention period.

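### Site, the randomisation stratum, is missing from the analysis, so the primary-endpoint t-test is conservative if drinking differs between sites

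*Combined protocol and SAP*

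**What the plan says.** Under Randomisation and blinding of allocation: "Six computer-generated randomisation sequences (one for each recruitment site) will be produced by a data scientist". Allocation is 1:1 in blocks of varying size between 2 and 6, and the plan draws the consequence itself: "As such, randomisation will be stratified by site". The access codes sent to participants come from a separate list for each site. Participants also report their service in the baseline survey.

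In the Data Analysis section, the primary analysis is introduced as follows: "A linear mixed-effects model (LMM) will be used to compare change in mean standard drinks consumed per week between groups across 4 time points". On its terms: "This model will test the main effects of time and group and (most crucially for determining efficacy) the group x time interaction". Group comparisons at the three post-baseline "time-points will be conducted using t-tests, with post-intervention being the primary endpoint".

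The Secondary outcomes paragraph handles the continuous outcomes in the same way. It compares past-month heavy drinking days, available only at post-intervention, by a t-test. Site is not mentioned in the Data Analysis section as a fixed effect, a random effect, a stratified test or a sensitivity analysis.

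**The concern.** Blocking within site makes the arms nearly equal in size at every site. A difference in average drinking between services then cannot move the arm difference, but an analysis that ignores site still counts that difference as noise. The reported standard error describes an unstratified trial and overstates the variability of the stratified one.

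This matters most for the post-intervention t-test. Hypothesis 1 concerns the level of weekly drinking at that time, and the plan makes it the primary endpoint. The sample size was set by practical limits, so precision that the design already provides should not be discarded. If site stays unmentioned, adding it later becomes a post hoc choice. The Interim analyses paragraph also allows student projects to work with the allocation known before the trial ends, which is a further reason to fix the model beforehand.

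**Working it through.** **Inputs from the documents.** Six sites; 1:1 allocation in blocks of 2 to 6; target of at least 300; four time points; alpha .05; 178 participants for 90% power at partial eta squared .01; 59% retention (178/300 = 59.3%).

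**Assumptions.** Site ICC .01 to .20, since the documents give none; two-sided tests, since sidedness is not stated; equal site sizes; random dropout; correlation between time points 0.5 and sphericity (epsilon = 1).

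**Step 1: the plan's own figure.** For the interaction, f² = .01/.99 = .0101 and lambda = f² × N × m/(1 − rho) = .0101 × 178 × 4/0.5 = 14.4, with 3 and 3 × 176 = 528 degrees of freedom. Power is 0.902. The minimum N is 177, or 178 for equal arms, so the stated figure reproduces. It depends on the assumed correlation: 0.4 gives 212 and 0.6 gives 142.

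**Step 2: the t-test at one time point, full retention.** Take total variance as 1, of which the ICC lies between sites. The t-test uses an error variance of 1, but the arm difference varies only with 1 − ICC. Therefore:

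- SE ratio: s = 1/√(1 − ICC)
- true alpha = 2 × [1 − Φ(1.96 s)]
- power without site, for an effect that the site-adjusted test detects with 90% power = Φ(3.24 − 1.96 s), where 3.24 = 1.96 + 1.28

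| Assumed ICC | SE too wide by | True alpha | Power without site (90% with site) |
|---|---|---|---|
| .01 | 0.5% | .049 | 89.8% |
| .05 | 2.6% | .044 | 89.1% |
| .10 | 5.4% | .039 | 88.0% |
| .20 | 11.8% | .028 | 85.3% |

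A simulation of 6 sites × 50 participants with blocks of 2, 4 and 6 (6,000 runs per setting) gave ratios of model SE to true SD of 1.026, 1.061 and 1.110 at ICC .05, .10 and .20, which agrees with the formula.

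**Step 3: 59% retention.** Dropout brings back some site imbalance, so the unadjusted SE is closer to the truth: the simulated ratios fall to 1.012, 1.050 and 1.059. A site term also removes that new imbalance. The unadjusted SE is still 2.0%, 4.8% and 11.1% larger than the site-adjusted one.

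**Step 4: the group x time test.** A constant site difference cancels from each participant's change. The simulated ratio of model SE to true SD for change from baseline was 0.996 to 1.007 for ICC .05 to .20, over both retention levels, with alpha near .05. The picture changes only if site differences move over time. With site x time variance assumed at 5% of the total at each time and a residual of 45%, the variance of change is 2 × .05 + 2 × .45 = 1.00. The site share is .10, so s = 1/√.90 = 1.054. Simulation gave an unadjusted/adjusted SE ratio of 1.054 and an alpha of about .042.

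**Step 5: which term repairs which test.** The mixed model was fitted with a random participant intercept, four times, ICC .10 and complete data (30 simulated trials per setting). With stable site effects, adding a site main effect left the mean SE of the interaction contrast at .1152. With the assumed site x time variance, a site main effect again changed nothing (.1198 both ways); adding site x time reduced it to .1157.

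**The case against.** The strongest reply is that the plan calls group x time the decisive test of efficacy, and Step 4 shows that stable site differences leave it untouched. That stands. A reader might infer that the mixed model's standard error is too wide whenever services differ in drinking, or that the 178 is wrong. The documents support neither reading: the interaction rests on within-participant change, and 178 was calculated for the interaction. A site main effect alone would not help that test even when site differences drift over time.

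It is also fair to say that the sentence on model terms lists what the model will test and is not a full specification; the random-effects and covariance structure is not given either. So the plan does not state that site is excluded. The supportable criticism is that its only stratification factor is not named.

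The effect may be small. At an ICC of .05 or below, the loss is under one point from 90% power, and nothing in the documents shows that larger values are likely. Finally, replacing the t-tests with model contrasts can be separated from adding site, because a site-adjusted comparison at each time point would also answer this concern.

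None of this rescues the unadjusted t-test at the primary endpoint, or the one for past-month heavy drinking days, where no baseline value of the same measure exists to remove site differences.

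**Conclusion.** The point holds for the single-time group comparisons, above all the post-intervention t-test. Their standard errors are too wide if mean drinking at that time differs between sites. The excess is 0.5% to 11.8% at full retention over an assumed ICC of .01 to .20, and less at 59% retention. A reader might take this as a threat of false positives, but the error runs the other way: the test operates below its nominal 5% level and power is lost. The group x time test is affected only by site differences that change over time, by about 5% under the variance assumed in Step 4. The sample size statement is not in question. The sizes rest on the assumed ICC, equal sites, two-sided tests and random dropout; the mismatch between allocation and analysis does not. This is a change the plan should make, and it does not threaten the validity of a positive result.

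**What to change.** In Data Analysis, Primary outcome, add a sentence: the mixed model will include recruitment site (the six-level randomisation stratum) and site x time as fixed effects, and the group differences at post-intervention, 1 month and 3 months will be estimated as contrasts from this model. If separate comparisons at each time point are preferred, adjust each for site.

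Apply the same rule to the secondary continuous outcomes. For past-month heavy drinking days, use a linear model with group and site in place of the t-test. Take site from the site-specific access-code lists, which define the stratum for every participant, and not from the self-reported survey item.

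The cost is one sentence, 5 degrees of freedom for site and 5 × 3 = 15 for site x time in the four-time-point model, with no new data, visits or participants.
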